This will be a prospective, randomized-controlled study in which qualified patients with partial edentulism will be treated with at least two dental implants. Implant sites will be randomly assigned to receive either a test (T3 Nanotite Certain Tapered Prevail - BNPT) or control (Nanotite Certain Tapered - NINTxx) implant (80:20 – test – control randomization ratio). All implants will be placed in a single-stage manner using torque-indicating instruments to document the torque-insertion profile. At implant placement surgery test implants will receive Encode healing abutments whereas control implants will be provisioned with prefabricated or standard abutments. For the test group an Encode Level Impression will take place at 10 weeks and individual final abutments and prosthesis placement at 3 months following implant placement surgery. A fixture level impression will be taken for control implants at week 10, followed by final restorations at month 3. All implants will be allowed to integrate without occluding forces and all restorations will be cemented. Resonance frequency assessment procedures will be done at implant placement surgery and at prosthesis insertion. Cumulative success rate and crestal bone regression will be the primary study endpoint. Enrollment will continue until 100 patients have completed final prosthetic treatment at the participating study centers. Additional control cases will be derived from on-going clinical trials of the NINT implants matched with the prospective study control group for baseline variables, restorative type (STR, fixed bridges), and implant dimensions. The additional control cases will bring the test and control groups to a 1:1 ratio and allow for more powerful analyses.

Study (null) hypothesis:

The functional success (survival and success rate) of the T3 implant to maintain integration and support of prostheses in this study will be no different than of the control implant. Moreover there crestal bone changes that take place after placement and loading of the T3 Certain Tapered Prevail (BNPTxxx – test implant) and Certain Tapered (NINTxx - control implant) will be the same.

[figure not shown]
MATERIALS AND METHODS

Implants with similar geometry but with different surface roughness will be evaluated. All implants are titanium root-form dental implants. The test implant has an integrated platform switch feature, whereas the restorative components of the control implant will be matched.

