While all implants are to be placed epicrestal if the depth of the osteotomy is over-prepared (e.g., the depth indicator shows that the osteotomy is 1 mm too deep) the implant should always be fully inserted into the osteotomy. If this results in a subcrestal placement this is preferred to a partially-placed implant. Therefore do not reverse or back-out the implant to have the seating surface epicrestal. Do not reverse or back-out the implant for any reason! It is better to be fully-seated in the osteotomy than to be epicrestal.

7. Proximity to teeth: Do not place an implant any closer than 1.5 mm from the crestal emergence margin of a proximal tooth.
8. Proximity to an adjacent implant: Do not place an implant any closer than 3 mm from the collar margin of a proximal implant.
9. Intra-ridge implant positioning: Please be mindful of placing the implant in the buccal-lingual center of the ridge to prevent loss of wall integrity. Whenever possible, select osteotomy positions that are equally distributed mesial-distally in the treatment region.
10. Conforming to the protocol's osteotomy preparation procedures: The drill sequence that is described in the study protocol is to be followed without exception. Please see the drill sequence chart in the Special Procedures section of this protocol. Do not undersize the osteotomy in soft bone conditions.
11. A case comprises all implants covered with one prosthesis. A case will consist of at least one implant with a crown.
12. Restorative cases will consist of single tooth restorations or unilateral short-span fixed prosthesis (<4implants). A patient can receive the maximum of two cases or 8 implants.
13. Cantilevers and pontics are not allowed in any of the study prostheses.
14. Test and control implants have different provisionalization procedures. A detailed description of the prosthetic procedures is part of the chapter "Specific procedures".
15. Temporary prosthesis are limited to flippers or resin bonded bridges for both test and control implants.

Schedule

Visit:	Follow-up Evaluations					
	1	2	3	4	5	6 - 11
	Screening	Day 0	Day 7	Week 10	Month 3	Months 6, 12, 24; 36; 48; 60

Dental / Medical History	X					
Clinical Evaluations		X	X	X	X	X
Randomization		X				
Implant Surgery		X				
Healing Abutment Placement		X				
Healing Assessment			X			
Impressioning				X		
Final Prosthesis Insertion					X	
Implant Mobility Assessment					X	X
RFA Analysis		X			X	
Radiography	PN	PA			PA	PA

PN = Panoramic radiograph

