A global evaluation of the status of the area where the study implants were placed will be recorded using gingival and plaque indices. The **gingival index** will be ranked as follows: (0) Normal gingiva; (1) Mild inflammation, slight change in color, slight edema, no bleeding on probing; (2) Moderate inflammation, redness, edema and glazing, bleeding on probing; (3) Severe inflammation, marked redness and edema, ulcerations; tendency toward spontaneous bleeding.

The criteria for **plaque index** are as follows: (1) No plaque in gingival area; (2) No plaque visible by the unaided eye, but plaque is made visible on the point of the probe after it has been removed across surface at entrance of gingival crevice; (3) Marginal area is covered with a thin to moderately thick layer of plaque; deposit is visible to the naked eye; (4) Heavy accumulation of soft matter, the thickness of which fills out a niche produced by gingival margin and tooth surface; interdental area is stuffed with soft debris.

EVALUATION CRITERIA

Implant Integration Success

An implant will be considered successful if it is immobile at specific points in time. Additionally, long-term implant success will be achieved when tested with instrument pressure at follow-up evaluations with no evidence of persistent peri-implant radiolucency, no persistent or irreversible signs and symptoms of pain, infection, neuropathies, or paresthesia.

Additionally the correlation of initial stability (as reflected in the Insertion Torque Profile) and clinical success will be assessed. The individual implant will be considered the experimental unit. The Insertion Torque Profiles for failed implants will be compared with those from successful implant cases to determine if this baseline variable is predictive.

Radiological Crestal Bone Level Changes

Bone levels measured at three and six month, and all follow-up intervals from both treatment groups will be compared to those measurements observed at the time of implant placement surgery to derive *changes from baseline* values. Differences between groups will be calculated and used to determine if the crestal bone changes are different between groups. A difference of 5% will be considered relevant.

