Secondary efficacy parameters will be prosthesis survival and procedural success. For each patient, survival time after study surgery will be calculated by the duration of failure-free, intervention-free, duration of support of a prosthesis. Implant survival curves will be estimated for the Test and Control treatment group and these will be compared using the Log Rank or Wilcoxon tests. Survival rates at six months (Study Visit 6), one-year (Study Visit 7) and 5 years (visit 11) will be computed for each treatment group, and compared using chi-square. The sample size determinations were based upon survival to the five-year point as a measure of efficacy.

A secondary outcome question of this study is the equivalence in the changes in alveolar crestal bone between the modified implant (T3) and its predecessor the Certain™ implant. In previous studies of Biomet3i implants (Calvo-Guirado 2011, Zetterqvist 2009; Östman et al. 2010), crestal bone change-from-baseline values have ranged from a mean of 0.37 mm to 1.2 mm at the six month (Visit 6) time point. For purposes of this study there will be an assumption that the control implant will have a change-from-baseline mean value of 0.75 mm at the 6 month (Visit 6) time period. To declare equivalence the Test implant system will need to have a crestal bone change-from-baseline mean bone level regression of 0.75 ± 0.15 mm; or to declare superiority a mean value of 0.55 mm or lower. For the functional evaluation of crestal bone regression will be determined for each of the treatment groups at 3 months (Visit 5), six months (Visit 6) and at each of the annual study visits. The significance of these changes from baseline will be evaluated at each time point using a paired t-test or a Wilcoxon signed rank test. At each time point the treatment groups will be compared using the analysis of variance or the blocked Wilcoxon test, as appropriate. Analysis to determine association with other variables will use “exact” rather than “asymptomatic” methods where necessary.

The Test and the Control implants will be considered the experimental units. The influence of the length and diameter of the implants as a covariate on survival will be determined during the analysis. The comparability of the Test and Control treatment groups will be determined with regard to demographic

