variables (including age, gender) and variables relating to the severity of disease (such as existing dental pathology and dental hygiene). For the continuous variables age and evaluations of oral hygiene and the gingival biotype, the groups will be compared using either analysis of variance or blocked Wilcoxon, as appropriate. For the qualitative variables, sex, smoking habit, existing dentition, concomitant conditions, a chi-square contingency table analysis will be used. Analysis to determine association with other variables will use "exact", rather than asymptotic methods where necessary.

All dental and medical events will be tabulated. Treatment groups will be compared using chi-square with regard to the number of patients in each group who experience those events most frequently and are assessed by the investigator as being probably or definitely related to the investigational treatment. Statistical significance will be declared if the two sided p-value is > 0.05 .

Calvo-Guirado JL, Gómez-Moreno G , López-Marí L, Guardia J, Negri B, Martínez-González JM. Crestal bone loss evaluation in osseotite expanded platform implants: a 5-year study. Clin Oral Impl Res 2011 21 MAR 2011
DOI: 10.1111/j.1600-0501.2010.02130.x

Östman PO, Wennerberg A, Albrektsson T. Immediate occlusal loading of NanoTite Prevail implants: a prospective 1-year clinical and radiographic study. Clin Implant Dent Relat Res. 2010 Mar;12(1):39-47.

Records / Data Retention

Case Report Forms (CRFs) will be prepared by 3i for the collection of data. These forms will be used for the entire duration of the study. The original of the completed CRF will continuously be collected by the study monitor for analysis and storage. Only original radiographs (or digital images saved on a disc) will be accepted and maintained by the study sponsor. Investigators will keep a copy of the CRFs and will maintain these records for at least three years.

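### Crestal bone change is compared between arms at seven post-baseline visits with no ranking, adjustment or exploratory label, so the chance of a false difference at some visit exceeds 5% (about 11% to 30% under assumed correlations)

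*Combined protocol and SAP*

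**What the plan says.** The Statistical Analyses section has crestal bone regression determined "at 3 months (Visit 5), six months (Visit 6) and at each of the annual study visits". The between-arm rule follows: "At each time point the treatment groups will be compared using the analysis of variance or the blocked Wilcoxon test, as appropriate". The Schedule lists the follow-up visits as "Months 6, 12, 24; 36; 48; 60", with periapical films at each, at Month 3 and on Day 0. Day 0 is the baseline.

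The Evaluation Criteria section (Radiological Crestal Bone Level Changes) repeats the plan: "Bone levels measured at three and six month, and all follow-up intervals from both treatment groups will be compared to those measurements observed". It then gives the comparisons a purpose: "Differences between groups will be calculated and used to determine if the crestal bone changes are different between groups". The bone part of the study (null) hypothesis says that the changes with the test implant and with the control ("NINTxx - control implant) will be the same") and attaches no visit to this.

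One significance level appears, at the end of the adverse-event paragraph: "Statistical significance will be declared if the two sided p-value is > 0.05". The inequality is printed the wrong way round.

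Month 6 has a special place. The control mean is assumed to be 0.75 mm at that visit, and two criteria follow. The first is "To declare equivalence the Test implant system will need to have a crestal bone change-from-baseline mean bone level regression of 0.75 ± 0.15 mm". The second allows superiority at a test mean of 0.55 mm or lower. The Statistical Analyses section calls bone change a secondary question, whereas the Study Design section puts it in the primary endpoint.

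**The concern.** The comparisons are meant to settle whether the arms differ, yet there are seven of them and the hypothesis does not say which one settles it. There is no testing order, no division of the 0.05 and no statement that any visit is only supportive. Someone writing the report could pick out any significant visit and cite the plan in support.

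Bone preservation is in the trial's title and, on one of the plan's two accounts, in the primary endpoint. A chance difference at one of seven visits could therefore carry real weight, in either direction.

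There is a second gap at Month 6 itself. The criteria there set the test mean against fixed values, while the between-arm test sets it against the observed control mean. The plan does not say how the two relate.

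**Working it through.** **No figure to reproduce.** The documents give no family-wise error rate, no between-visit correlation and no standard deviation for bone change.

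**Inputs from the documents**
- Number of comparisons: Months 3, 6, 12, 24, 36, 48 and 60, so k = 7 (Statistical Analyses and Schedule).
- Level: two-sided 0.05, read as p < 0.05 and applied to the bone tests. This is an inference, given where the sentence sits and how it is printed.

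**Assumptions**
- No true difference at any visit.
- A significant result at any visit is read as a difference.
- Each test has a true size of 5%.
- Between-visit correlation of the test statistics as tabulated.

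**Chance of at least one false difference**

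Independent visits: 1 − 0.95^7 = 0.302.

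For a common correlation ρ, the result is 1 − ∫ φ(x) [Φ((c − √ρ·x)/√(1−ρ)) − Φ((−c − √ρ·x)/√(1−ρ))]^7 dx, with c = 1.96. The last column counts only false findings in favour of the test implant. It drops the second Φ term, and the nominal value for one test is 2.5%.

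| ρ | Any false difference | Favouring test |
|---|---|---|
| 0 | 30.2% | 16.2% |
| 0.3 | 27.2% | 13.7% |
| 0.5 | 23.0% | 11.5% |
| 0.7 | 17.8% | 8.9% |
| 0.8 | 14.9% | 7.4% |
| 0.9 | 11.4% | 5.7% |

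If correlation instead decays with distance (first-order autoregressive between adjacent visits, 500,000 simulated draws), the any-difference rate is 26.7% at 0.5, 22.4% at 0.7, 19.2% at 0.8 and 14.7% at 0.9.

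**Not counted.** The choice between analysis of variance and Wilcoxon is left open, bone loss is expressed both as an absolute and as a normalised value, and implants are the analysis unit although patients are randomised. Each could raise the error further.

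**Conflict within Month 6**

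Take 200 implants split 80:20, so 160 test and 40 control, treated as independent. The smallest significant difference is 1.96 × SD × √(1/40 + 1/160):
- SD 0.3 mm (assumed): 0.10 mm
- SD 0.5 mm (assumed): 0.17 mm
- SD 0.7 mm (assumed): 0.24 mm

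The equivalence range is 0.75 ± 0.15, or 0.60 to 0.90 mm. At SD 0.3, a control mean of 0.75 and a test mean of 0.64 differ by 0.11 mm. That is significant, and the test mean is also inside the equivalence range. At SD 0.5 or 0.7 this cannot happen with the control mean at 0.75, because the test mean can then differ by at most 0.15 mm. It can at SD 0.5 if the control mean moves: control 0.85 and test 0.65 differ by 0.20 mm.

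**After the fix.** One confirmatory visit, or Month 6 then Month 60 in fixed order, holds the bone error at 5% for a test of true 5% size. A Bonferroni split would need 0.05/7 = 0.00714 per visit.

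**The case against.** Much can be said for the plan. It names implant survival as the primary efficacy parameter, calls bone a secondary question and attaches its only bone criteria to Month 6. So there is some hierarchy, and it would be wrong to say there is none. What is missing is a ranking across visits. The conflicting endpoint status in the Study Design section is a separate defect.

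No sentence says that a single significant visit rejects the hypothesis. The Evaluation Criteria section also adds a 5% relevance threshold. The any-visit rule is a reading of a hypothesis without a visit and of comparisons meant to decide the matter. It is a natural reading, but not a stated rule.

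High correlation is plausible, because every value is a change from the same surgical film on the same implant. That favours the lower part of the range. Even at 0.9 the rate is more than twice 5%.

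A reader might infer that equivalence at Month 6 and a difference at Month 24 contradict each other. They do not: results at different times can both be true. A reader might also infer that a chance p-value lets the sponsor declare superiority. As written, superiority needs a test mean of 0.55 mm or lower, so a small p-value at some visit is not enough.

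**Conclusion.** The concern stands in a limited form. The plan sets seven between-arm bone comparisons, uses them to decide whether the arms differ, and does not say which visit decides. If each is tested at two-sided 0.05 and any significant visit is read as a difference, the false-positive chance is about 11% to 30% for correlations from 0.9 down to 0, and about half of those findings would favour the test implant.

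A reader might take 23% as this plan's error rate. The documents do not support one figure: 23% needs an assumed common correlation of 0.5. The 0.05 level and the any-visit reading are also inferences. That the rate exceeds 5% does not depend on which of the tabulated correlations is right.

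The Month 6 conflict is a separate gap, not a multiplicity effect. Whether it would arise in practice depends on the unknown standard deviation and on the observed control mean.

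**What to change.** 1. Name the Month 6 (Visit 6) between-arm difference in change from baseline as the single confirmatory bone comparison, and add that visit to the bone part of the null hypothesis.
2. Restate the Month 6 criteria in terms of that difference. The plan's own figures translate to a margin of ±0.15 mm for equivalence and a reduction of 0.75 − 0.55 = 0.20 mm for superiority; the sponsor should confirm that this is what was meant. State the confidence interval to be used, and which conclusion stands if the interval lies inside the margin but excludes zero.
3. Report Months 3, 12, 24, 36, 48 and 60 as between-arm differences with 95% confidence intervals, labelled exploratory. If a long-term claim is wanted, test Month 60 at 0.05 only after Month 6 succeeds, with success defined in advance.
4. Correct the inequality in the significance sentence and say which analyses it governs.

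This changes wording in the null hypothesis, the Evaluation Criteria and the Statistical Analyses, and needs no further patients or data. The cost is that an isolated difference at another visit could be described but not claimed.

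### The plan's only p-value threshold is printed with the inequality reversed, and the tests it covers are not stated

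*Combined protocol and SAP*

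**What the plan says.** The last paragraph of Statistical Analyses deals with dental and medical events. It says: "Treatment groups will be compared using chi-square with regard to the number of patients in each group who experience those events most frequently", limited to events that the investigator judges probably or definitely related to treatment. The next sentence, which ends the analysis text, is "Statistical significance will be declared if the two sided p-value is > 0.05".

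Earlier in the section several tests are named without a threshold of their own:

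- Implant survival curves: "these will be compared using the Log Rank or Wilcoxon tests".
- Survival rates at six months, one year and five years: "will be computed for each treatment group, and compared using chi-square".
- Crestal bone change within each group: "The significance of these changes from baseline will be evaluated at each time point using a paired t-test or a Wilcoxon signed rank test".
- Crestal bone change between groups, and baseline comparability: analysis of variance or a blocked Wilcoxon test, with chi-square for qualitative baseline variables.

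The section also has decision criteria that use no p-value. For crestal bone these are an equivalence range of 0.75 ± 0.15 mm and, "to declare superiority a mean value of 0.55 mm or lower". Survival differences above 5% are called clinically relevant. Under Evaluation Criteria, a 5% difference in bone change is called relevant.

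**The concern.** The null hypothesis under Study Design is that test and control implants do not differ in survival, success or crestal bone change. A small p-value is evidence against that hypothesis, so a rule that declares significance for large p-values is back to front.

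The sentence matters because it is a decision threshold and no other p-value threshold or confidence level appears in the text. For safety, a clear excess of related events on the test implant (p below 0.05) would be recorded as not significant. If the sentence is the rule for the whole section, the same reversal reaches the tests of the primary survival endpoint.

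**Working it through.** The plan gives no figure to reproduce here: it states no power, event rate, standard deviation (SD) or alpha for its sample size. The check is therefore on the rule itself.

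**1. No true difference.** A continuous p-value is then uniform on (0, 1), so P(p > 0.05) = 1 − 0.05 = 0.95. A simulation of 1,000,000 null z-tests gave 0.950. With the sign corrected, the rate is 0.05. For chi-square or exact tests on few failures, p-values are discrete and these rates are approximate.

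**2. A true difference.** P(declared significant as written) = 1 − power.

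- Assumed power 80%: 1 − 0.80 = 20%.
- Assumed power 90%: 1 − 0.90 = 10%.
- Assumed power 50%: 1 − 0.50 = 50%, the same as under the corrected rule.
- Power below 50%: the written rule declares significance more often than the corrected one, but for the wrong reason.

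**3. Illustration with the plan's own bone figures.** Inputs:

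- Control mean at six months, from Statistical Analyses: "the control implant will have a change-from-baseline mean value of 0.75 mm". The superiority cut-off is 0.55 mm, so the difference is 0.75 − 0.55 = 0.20 mm.
- 100 patients with at least two implants each, randomized 80:20 (Patient Sample; Randomization). That gives 80 test and 20 control patients, or 160 and 40 implants. Adding outside controls to reach 1:1, as Study Design plans, gives 160 and 160.
- SD: not in the documents, so assumed to be 0.3 to 1.0 mm.
- Observations treated as independent, two-sided alpha 0.05.

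Standard error = SD × √(1/n_control + 1/n_test). Power = Φ(0.20/SE − 1.96) + Φ(−0.20/SE − 1.96). For 40 and 160 implants with SD 0.3 mm, SE = 0.3 × √(1/40 + 1/160) = 0.053, 0.20/SE = 3.77 and power = Φ(1.81) = 96.5%.

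Chance of declaring the 0.20 mm difference significant, corrected rule / rule as written:

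| Control : test | SD 0.3 mm | SD 0.5 mm | SD 0.7 mm | SD 1.0 mm |
|---|---|---|---|---|
| 40 : 160 implants | 96.5% / 3.5% | 61.9% / 38.1% | 36.6% / 63.4% | 20.5% / 79.5% |
| 20 : 80 patients | 76.0% / 24.0% | 36.0% / 64.0% | 20.8% / 79.2% | 12.6% / 87.4% |
| 160 : 160 implants | >99.9% / <0.1% | 94.7% / 5.3% | 72.4% / 27.6% | 43.2% / 56.8% |

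The table concerns the between-group test of bone change, not the 0.55 mm cut-off, which is applied to the mean without a p-value.

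**4. Scope, from the text.** The rule follows directly on the adverse-event chi-square comparison and nothing in the text extends it to the earlier tests. There are two readings:

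- Wide: it is the closing rule of the section, and every p-value comparison in the section is reversed.
- Narrow: it covers adverse events only. That comparison is reversed, and the survival, bone and baseline tests have no stated significance level.

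The sentence needs correction under either reading.

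**The case against.** The strongest reply is that this is an obvious slip. The section is loosely edited (it has *asymptomatic* where *asymptotic* is meant), and a reference to statistical significance, a two-sided p-value and 0.05 leaves little doubt about intent. No analyst is likely to report p = 0.60 as significant. This stands: the 95% figure measures the literal sentence, not the error the trial is likely to make.

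A fault in reading the PDF cannot be fully excluded. It is unlikely, because the same text gives sensible signs for the smoking exclusion, the limit on implants per prosthesis and the survival relevance threshold. A look at the source file settles it.

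A reader might infer that every efficacy and safety conclusion is inverted. The documents do not support that. The crestal bone equivalence and superiority cut-offs and the two 5% relevance thresholds use no p-value, and the survival fractions and event tabulations are descriptive. Whether the sentence governs the survival and bone tests at all is an inference from its position.

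A reader might also infer that real differences would never be declared. That is close to true only when power is high, as the table shows.

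Finally, because the plan speaks of no difference and of equivalence, the sign could be taken as a deliberate equivalence rule. The sentence declares significance, not equivalence, and failure to reject a hypothesis of no difference would not show equivalence anyway.

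**Conclusion.** The threshold is wrong as written. It is the only p-value threshold in the plan, and no other text corrects it. Taken literally, the false-positive rate per test is about 95% instead of 5%, and the chance of declaring a true difference is the complement of power. The 95% needs only a continuous p-value. The figures for a true difference rest on assumed power or SD.

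The adverse-event comparison is directly affected. The survival, crestal bone and baseline tests are either reversed too or left without a significance level, depending on how far the sentence reaches. The realistic harm is an invalid and ambiguous prespecified criterion rather than an analysis actually run backwards. It still needs correcting, because a prespecified rule should not depend on readers silently reversing it.

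**What to change.** Check the sign against the source file, then replace the sentence with: *For all survival, crestal bone, baseline and adverse-event comparisons, a result is called statistically significant when the two-sided p-value is less than 0.05.* Add: *A p-value of 0.05 or more is not in itself evidence of equivalence.*

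This corrects the direction, keeps the test two-sided and settles which comparisons are covered. It leaves the crestal bone cut-offs and the 5% relevance thresholds as they are; whether those are adequate is a separate question.

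The cost is one replaced sentence and one added note, issued by the addendum or revised protocol described under Protocol Amendments. It requires no change to sample size, visits or data collection.
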